## 10.4 STATISTICAL APPENDIX

A BLRM with overdose control will be used to guide dose escalation in the SRD part of this study. The BLRM is introduced in [Section 7.2](#), which also specifies the prior for the model. After patients in each cohort have completed the evaluation period of 7 days, the prior distribution will be updated through Gibbs sampling procedures with the accumulated DLE data from the evaluation period. Posterior probabilities for the rate of DLEs will be summarised from the BLRM. Selection of the next dose will be based on these probabilities as well as on other safety and laboratory data.

The purpose of this statistical appendix is to present performance metrics (operating characteristics) that illustrate the precision of the design in estimating the MTD (see

Section 3.1) under various dose-toxicity relationships through computer simulation. These results are summarized in [Table 10.4: 3](#). In addition, recommendations of the next dose level by the BLRM with overdose control principle are provided under various hypothetical outcome scenarios, to show how it facilitates on-study dose-escalation decisions (see [Table 10.4: 1](#)). For simplicity reasons, a cohort size of 3 patients who are all evaluable is assumed.

#### Hypothetical data scenarios

Hypothetical data scenarios are shown in [Table 10.4: 1](#). These scenarios reflect potential on-study data constellations and related escalation as allowed by the model and the planned dose groups. It is assumed that each cohort has exactly three patients who are all evaluable. For each scenario, the probability of overdose for the current dose, as well as the next potential dose and related probabilities of target dosing and over-dosing are shown (probability of over-dosing: P(OD), probability of target dosing: P(TD)).

For example, scenario 1 represents the case that no DLE is observed in 3 patients at the starting dose of 0.3 mg. In this case, the next planned dose permitted by the model and the 233% escalation rule is 1 mg. In contrast, scenario 2 assumes that there is one DLE observed in the first dose group. This would mean overtotoxicity from the beginning, i.e., all planned dose levels are not considered safe.

In scenario 3, there is no DLE after the first 2 dose groups, which would allow the trial to continue to the next dose level. If no further DLE occurs in the trial, dose escalation would proceed to the 6 mg dose, with an additional cohort at that dose level at the end of the SRD part, i.e. overall 15 patients (scenario 3b).

In scenario 4, the first DLE occurs in dose group 1 mg. Then the recommendation would be to treat an additional cohort of 3 patients at the same dose level. If no new DLE occurs then, scenario 4b shows that the next recommended dose level would still be 1 mg. Thus, the 1 mg dose would be declared as MTD and the SRD part of the trial would stop (after 9 patients).

However, if (after repeating dose group 1 mg according to the recommendation from scenario 4) there was another DLE in the second cohort for dose group 1 mg (as in scenario 5), then the recommendation would be to go back to dose 0.3 mg. If there was no further DLE then (scenario 5b), one could go up again to dose 1 mg. If there was no further DLE then, the SRD part of the trial would stop after 15 patients, declaring 1 mg as MTD (scenario 5c).

Scenario 6 shows the case where the first DLE occurs in the 3 mg dose group. Then an additional cohort of 3 patients would have to be treated at this dose level. If these 3 patients have no further DLE, the next recommended dose would still be 3 mg. Thus, 3 mg would be declared as MTD, after 12 patients (scenario 6b).

In scenario 7, there is the first DLE in the first cohort of the 6 mg dose group. Then the dose would have to be reduced to 3 mg for the next cohort. In case of no further DLE, the SRD part of the trial could stop after 18 patients overall (scenarios 7b, 7c).

In contrast, if the first DLE occurs only in the second cohort of dose group 6 mg (scenario 8), then the SRD part of the trial could still be completed with a total of 15 patients. However, if there were 2 DLEs in the highest dose group, then the model would recommend to return to dose 3 mg (scenario 9).

Table 10.4: 1 Hypothetical data scenarios

Scenario	Dose (mg/eye)	# Pat.	# DLE	Current Dose: P(OD)	Next recomm. Dose (mg/eye)	Next dose:	
						P(TD)	P(OD)
1	0.3	3	0	0.015	1	0.960	0.040
2	0.3	3	1	0.309	N/A	N/A	N/A
3	0.3 1	3 3	0 0	0.012	3	0.963	0.064
3b	0.3 1 3 6	3 3 3 6	0 0 0 0	0.013	6	0.987	0.013
4	0.3 1	3 3	0 1	0.202	1	0.798	0.202
4b	0.3 1	3 6	0 1	0.077	1	0.923	0.077
5	0.3 1	3 6	0 2	0.313	0.3	0.894	0.106
5b	0.3 1	6 6	0 2	0.047	1	0.776	0.224
5c	0.3 1	6 9	0 2	0.109	1	0.891	0.109
6	0.3 1 3	3 3 3	0 0 1	0.218	3	0.782	0.218
6b	0.3 1 3	3 3 6	0 0 1	0.088	3	0.912	0.088
7	0.3 1 3 6	3 3 3 3	0 0 0 1	0.253	3	0.960	0.040
7b	0.3 1 3 6	3 3 6 3	0 0 0 1	0.016	6	0.806	0194

Table 10.4: 1 Hypothetical data scenarios (cont'd)

Scenario	Dose (mg/eye)	# Pat.	# DLE	Current Dose: P(OD)	Next recomm. Dose (mg/eye)	Next dose:	
						P(TD)	P(OD)
7c	0.3	3	0	0.085	6	0.915	0.085
	1	3	0				
	3	6	0				
	6	6	1				
8	0.3	3	0	0.113	6	0.887	0.113
	1	3	0				
	3	3	0				
	6	6	1				
9	0.3	3	0	0.364	3	0.944	0.056
	1	3	0				
	3	3	0				
	6	6	2				

### Operating characteristics

Operating characteristics are a way to assess the long-run behaviour of a model by illustrating the precision of the design in estimating the MTD. Under an assumed true dose-toxicity curve, metrics such as the probability of recommending a dose with true DLE rate in the target interval can be approximated via simulation. [Table 10.4: 2](#) describes 6 assumed true dose-toxicity scenarios which were used to assess the operating characteristics of the model.

These scenarios reflect a wide range of possible cases as follows:

- Scenario 1: aligned with prior medians
- Scenario 2: aligned with prior means
- Scenario 3: high-toxicity scenario
- Scenario 4: low-toxicity scenario
- Scenario 5: non-logistic dose-toxicity scenario
- Scenario 6: low-toxicity followed by high-toxicity

Table 10.4: 2

Assumed true dose-toxicity scenarios

Scenario	DLE rate, P(DLE)	Dose (mg)			
		0.3	1	3	6
1: Prior Med	DLE rate, P(DLE)	0.007	0.017	0.048	0.101
2: Prior Mean		0.067	0.096	0.147	0.212
3: High Tox		0.100	0.150	0.400	0.600
4: Low Tox		0.001	0.005	0.010	0.100
5: Non-Logistic		0.050	0.010	0.200	0.500
6: Low-High		0.010	0.050	0.400	0.600

For each of these scenarios, 1000 trials were simulated. Each cohort consisted of 3 patients and dose escalation complied with the following rule:

*Escalate to the maximum dose which satisfies the overdose criterion and is  $\leq 234\%$  increase from the current dose.*

The MTD was considered reached if at least 6 patients have been evaluated at a dose level which is the model's recommendation for the next dose cohort. The maximum allowed patient number for each trial was chosen as 18 or 21.

It was then assessed how often a dose was declared as MTD with true DLE rate in the targeted or in the overdosing range. Furthermore, the average, minimum and maximum number of patients per trial and the average number of DLEs per trial are reported. Results are shown in [Table 10.4: 3](#).

Table 10.4: 3

Simulated operating characteristics

Scenario	Max. allowed # Patients	% of trials declaring a MTD with true DLE rate in		% of stopped trials**	# Patients	# DLEs
		[0, 0.25] target dosing	[0.25,1] overdosing			
1*	18	87.3	0.7	12.0	16.5 (3-18)	1.99 (0-6)
2*	18	67.9	0.1	32.0	12.2 (3-18)	1.79 (0-6)
3	18	60.1	9.0	30.9	11.5 (3-18)	2.17 (1-6)
4*	18	85.7	1.9	12.4	17.6 (3-18)	1.91 (0-6)
5	18	69.7	3.6	26.7	13.1 (3-18)	1.97 (0-6)
6	18	73.5	15.0	11.5	13.3 (3-18)	2.27 (1-6)
1*	21	96.8	0.5	2.8	16.7 (3-21)	2.01 (1-7)
2*	21	77.0	0.2	22.8	12.7 (3-21)	1.86 (1-7)
3	21	65.8	9.1	25.1	12.2 (3-21)	2.33 (0-7)
4*	21	97.8	1.4	0.8	17.9 (3-21)	1.95 (0-6)
5	21	76.7	4.7	18.6	13.8 (3-21)	2.06 (0-6)
6	21	77.4	14.1	8.5	13.8 (3-21)	2.40 (0-6)

\* Due to technical reasons, scenarios 1,2, and 4 could only be calculated with one additional dose level with assumed true DLE rate in the overdose range. As additional dose level, a dose of 15mg was chosen with the following assumed true toxicity probabilities: scenarios 1,2: 0.7, scenario 4: 0.6.

\*\* The stopped trials include early stopped trials (stopped due to too much toxicity), as well as trials that stopped because the maximum allowed patient number was reached before an MTD was found.

#### Maximum number of patients =21

The case when the maximum number of patients is chosen as 21 allows the model to appropriately perform in most cases and for finding an MTD within the target dosing range with very high probability.

In scenario 1, which reflects the case that the true dose-toxicity is aligned with prior medians, 96.8% of the simulated trials declared a dose as MTD with true DLE rate in the targeted toxicity range. Note that 2.8% of the simulated trials stopped either because there was no MTD determined after 21 patients had been observed (0.5%) or because of too high toxicity for the planned doses (2.3%). This latter is mostly due to the cases that 1 DLE is observed out of 3 patients at the starting dose of 0.3 mg. In reality, this situation would rarely happen as the safety profile of starting dose is expected to be good.

In scenario 2, the assumed dose toxicities are higher than in scenario 1. This results in a higher percentage of early stopped trials (about 23%). In this case, about 77% of the trials would end with an estimated MTD within the targeted toxicity range, and 0.2% in the overdosing range.

In Scenario 3 (high-toxicity scenario), only 65.8 % of the trials declared a dose as MTD with true DLE rate in the targeted toxicity range. In 9.1% of the trials, the estimated MTD was in

the overdosing range. Scenario 4 (low-toxicity scenario) shows the best results, i.e. the lowest number of stopped trials and the highest number of trials with estimated MTD in the target range, as would be expected.

Scenarios 5 and 6 showed reasonable operating characteristics, given the quite large deviations of the assumed true dose-toxicity curve from the assumptions underlying the BLRM.

The mean patient numbers range from 12.2 patients (Scenario 3) to 17.9 patients (Scenario 4), and the maximum number of patients was 21. Therefore, the patient numbers are as expected and increase when moving away from the high-toxicity scenario.

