### 7.2 PLANNED ANALYSES

#### 7.2.1 General considerations

##### 7.2.1.1 Dose escalation in the SRD part

The dose escalation will be guided by a Bayesian 2-parameter logistic regression model with overdose control [[R13-4803](#), [R13-4806](#)]. For a given dose, the EWOC criterion is that there should be less than 25% risk that the true ocular and systemic DLE rate is above 0.25. The BLRM will not be used for the analysis of the primary endpoint.

The model is given as follows:

$$\text{logit}(\pi_d) = \log(\alpha) + \beta * \log(d/d^*),$$

where  $\text{logit}(\pi) = \log(\pi/(1-\pi))$ ,  $\pi_d$  represents the probability of having a DLE in the evaluation period at dose  $d$ ,  $d^* = 6$  mg is the reference dose, allowing for the interpretation of  $\alpha$  as the odds of a DLE at dose  $d^*$ , and  $\theta = (\log(\alpha), \log(\beta))$  with  $\alpha, \beta > 0$  is the parameter vector of the model.

The estimated probability of a DLE at each dose level from the model will be summarized using the following intervals:

Target toxicity: [0.00, 0.25]

Over toxicity: [0.25, 1.00]

The BLRM-recommended dose for the next cohort is the dose level with the highest posterior probability of the DLE rate falling in the target interval [0.00, 0.25] among the doses fulfilling EWOC. Thus, it should be unlikely (< 25% posterior probability) that the DLE rate at that dose will exceed 0.25. However, the maximum allowable dose increment for the subsequent cohort will be no more than 233% from the previous dose up to doses of 3 mg, and to a maximum of 100% from the previous dose from dose 3 mg onwards. Dose escalation will continue up to the 6 mg dose as long as the EWOC criterion for the next dose level is fulfilled. At the final dose, at least 6 treated patients are required. However, the SMC may decide to include an additional number of patients at this dose level.

Since a Bayesian approach is applied, a prior distribution  $f(\theta)$  for the unknown parameter vector  $\theta$  needs to be specified. This prior distribution will be specified as a mixture of three multivariate normal distributions, i.e.

$$f(\theta) = a_1 f_1(\theta) + a_2 f_2(\theta) + a_3 f_3(\theta)$$

with  $a_i$ ,  $i = 1, 2, 3$  the prior mixture weights ( $a_1 + a_2 + a_3 = 1$ ), and  $f_i(\theta) = \text{MVN}(\mu_i, \Sigma_i)$ , the multivariate normal distribution of the  $i$ -th component with mean vector  $\mu_i$  and covariance matrix  $\Sigma_i$ , where

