### **7.5 DETERMINATION OF SAMPLE SIZE**

#### SRD part:

If no DLE occurs, 15 DLE evaluable patients will be treated in this trial part, based on the planned number of dose levels that are tested and on the requirement to have 6 DLE evaluable patients in the last dose group (see [Section 3.1](#)). However, the actual number of patients will depend on the actual number of dose cohorts tested and on the occurrence of DLEs. Based on the simulation study to evaluate operating characteristics of the BLRM (see [Appendix 10.4](#)), about 17 evaluable patients are expected to be treated in the dose escalation part for the model to have reasonable operating characteristics relating to its MTD recommendation.

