#### Maximum number of patients =18

If the maximum number of patients is chosen as 18, an early stopping of the trial would be more often required than above. In most cases, this would be due to reaching the maximum number of patients before an MTD could be determined. Still, the resulting operating characteristics are reasonable.

The mean patient numbers range from 11.5 patients (Scenario 3) to 17.6 patients (Scenario 4), and the maximum number of patients was 18. Again, the patient numbers are as expected and increase when moving away from the high-toxicity scenario.

Overall, by reviewing the metrics presented in [Table 10.4: 3](#), it can be seen that the model is generally conservative due to the overdose control criteria. In all scenarios, the probabilities of recommending a dose with true DLE rate being at least 25%,  $P(DLE \geq 25\%)$ , as MTD are much smaller than the probabilities of recommending a dose with true  $P(DLE) < 25\%$  as MTD.

R version 3.5.1 was used for data scenarios and simulations.

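### Protocol Appendix 10.4: the Scenario 3 (high-toxicity) results at a maximum of 21 patients do not follow from the DLE rates stated for that scenario

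*Protocol*

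**What the plan says.** Table 10.4: 2 in Protocol Appendix 10.4 gives the Scenario 3 true DLE rates at 0.3, 1, 3 and 6 mg as "0.100 0.150 0.400 0.600". For a maximum of 21 patients, Table 10.4: 3 reports 65.8% of trials declaring an MTD in the target range, 9.1% in the overdosing range and 25.1% stopped, with a mean of 12.2 patients. The text repeats the first figure: "In Scenario 3 (high-toxicity scenario), only 65.8 % of the trials declared a dose as MTD" in that range. Stopped trials include both toxicity stops and trials that reach the patient cap without an MTD.

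The rules that drive the simulation are also stated:

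- Section 7.2.1.1 sets the overdose criterion: "there should be less than 25% risk that the true ocular and systemic DLE rate is above 0.25".
- The simulation moves to the highest dose that meets this criterion within a 234% increment, in cohorts of 3, with 1000 trials per scenario.
- On the MTD: "The MTD was considered reached if at least 6 patients have been evaluated at a dose level" that the model recommends next.
- After 1 DLE in 3 patients at 0.3 mg, hypothetical data scenario 2 gives P(OD) 0.309 and says "all planned dose levels are not considered safe".
- The text on simulated Scenario 1 attributes its toxicity stops to the same event: "mostly due to the cases that 1 DLE is observed out of 3 patients at the starting dose of 0.3 mg".

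**The concern.** With a true rate of 0.10 at the starting dose, more than a quarter of trials should end after the first cohort. The published total for all stops, whatever the cause, is lower than that. Scenario 3 is the only row at the 21-patient cap whose stopped percentage lies below its own first-cohort figure.

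If the row is wrong, the protocol misstates how the design behaves in the one scenario it labels high-toxicity. The 65.8% is quoted in the text, the mean of 12.2 is the lower end of the stated range of patient numbers, and Section 7.5 rests its sample-size discussion on this work ("Based on the simulation study to evaluate operating characteristics of the BLRM").

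**Working it through.** **Inputs.** The three-component prior, the reference dose of 6 mg and the overdose criterion come from Section 7.2.1.1. The true rates, cohort size, increment rule, MTD rule and caps come from Appendix 10.4. Following the footnote to Table 10.4: 3, a 15 mg level is added for Scenarios 1, 2 and 4.

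**Method.** The posterior was computed on a grid, and every path of 3-patient cohorts was enumerated exactly, so the results below carry no simulation error.

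**Check against the plan's own posteriors.** P(OD) at 0.3 mg after 1/3 at that dose is 0.313 (plan 0.309). Prior P(OD) at the four doses is 0.082, 0.124, 0.201 and 0.306 (plan 0.083, 0.124, 0.201 and 0.304). The current-dose P(OD) values in Table 10.4: 1 agree within about 0.011, and all next-dose recommendations match.

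**Hand check, step 1: first-cohort stops.** The probability of at least one DLE in 3 at rate p is 1 − (1 − p)³.

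| Scenario | Rate at 0.3 mg | First-cohort stop % | Published total stopped %, cap 21 |
|---|---|---|---|
| 1 | 0.007 | 2.1 | 2.8 |
| 2 | 0.067 | 18.8 | 22.8 |
| **3** | **0.100** | **27.1** | **25.1** |
| 4 | 0.001 | 0.3 | 0.8 |
| 5 | 0.050 | 14.3 | 18.6 |
| 6 | 0.010 | 3.0 | 8.5 |

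The 2-point shortfall in Scenario 3 could by itself be simulation error: P(251 or fewer stops in 1000 at 27.1%) is about 0.08.

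**Step 2: add second-cohort stops.** After 0/3 at 0.3 mg and 2/3 at 1 mg, P(OD) at 0.3 mg is 0.28, above the 0.25 limit, so no dose is allowed; 3/3 is worse. The added probability is 0.9³ × (3 × 0.15² × 0.85 + 0.15³) = 0.729 × 0.06075 = 4.4%. The floor becomes 27.1 + 4.4 = 31.5%. With a standard error of √(0.315 × 0.685 / 1000) = 1.5 points, 25.1% lies 4.4 standard errors below it.

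**Step 3: all paths.** Total toxicity stops are 33.7 to 33.9%. P(251 or fewer in 1000 at 33.7%) is about 2e-9.

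**Full results at cap 21.** The MTD rule can be read in two ways: declared only when the recommended dose is also the dose just given (current-dose), or at any recommended dose that already has 6 patients (as printed). Entries are target / overdose / stopped %.

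| Scenario | Published | Current-dose | As printed |
|---|---|---|---|
| 1 | 96.8 / 0.5 / 2.8 | 97.4 / 0.3 / 2.3 | 97.4 / 0.3 / 2.2 |
| 2 | 77.0 / 0.2 / 22.8 | 77.1 / 0.1 / 22.8 | 78.1 / 0.1 / 21.8 |
| **3** | **65.8 / 9.1 / 25.1** | **55.1 / 7.8 / 37.0** | **57.0 / 9.3 / 33.7** |
| 4 | 97.8 / 1.4 / 0.8 | 98.1 / 1.6 / 0.3 | 98.1 / 1.6 / 0.3 |
| 5 | 76.7 / 4.7 / 18.6 | 77.7 / 3.7 / 18.6 | 82.0 / 3.7 / 14.3 |
| 6 | 77.4 / 14.1 / 8.5 | 76.7 / 15.0 / 8.3 | 77.5 / 18.7 / 3.8 |

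The current-dose reading reproduces the other five rows within 1.0 point on target and 0.5 point on stopped. In Scenario 3 it misses by 65.8 − 55.1 = 10.7 and 37.0 − 25.1 = 11.9 points; the printed rule misses by 8.8 and 8.6. Mean patients in Scenario 3 are 10.6 (current-dose) or 10.0 (as printed), against 12.2 published.

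**Sensitivity.** Moving the overdose cutoff between 0.24 and 0.26, to mimic sampling noise in the posterior, keeps Scenario 3 within 55.1 to 57.5% target, 33.7 to 37.1% stopped and mean N 10.0 to 10.6. With random error of SD 0 to 0.04 added to P(OD), no batch of 1000 simulated trials (20 batches per setting) had target above 61.7% or stopped below 27.9%. Continuing at 0.3 mg after a failed criterion, or raising the cutoff to 0.32, overshoots (72 to 79% target, 12 to 15% stopped), contradicts hypothetical scenario 2 and breaks other rows.

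**The case against.** The strongest reply concerns weight. All SRD cohorts are complete with no DLE reported (Section 1.2), the BLRM is not used for the primary endpoint, and the MD part does not use it. The figure of about 17 patients in Section 7.5 matches Scenarios 1 and 4, so correcting Scenario 3 would not move the sample size. The protocol's conclusion that overdosing recommendations are much rarer than target ones also survives: about 8 to 9% against 55 to 57%. All of this stands, and it limits the consequence. It does not make the row correct.

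A second reply is that the sponsor's code and sampler settings are not visible and that the re-derivation is less exact at the 18-patient cap, where the current-dose reading misses other rows by up to about 5 points (Scenario 5). That is fair for cap 18. There the published Scenario 3 row (60.1 / 9.0 / 30.9%, mean 11.5) compares with 52.3 / 7.1 / 40.6% (current-dose) or 56.7 / 9.2 / 34.1% (as printed), so the gap depends on the reading and no separate error is claimed. It does not help at cap 21, where the calculation is calibrated on five rows and toxicity stops alone exceed the published total under both readings.

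Third, the two readings are not equally supported. Hypothetical scenarios 5b and 5c treat a further cohort at 1 mg although that dose already has 6 patients and is recommended, which favours the current-dose reading. That points to the larger of the two gaps.

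**Conclusion.** The point holds. Table 10.4: 2 and Table 10.4: 3 cannot both be right for Scenario 3. Taking the tabulated rates as given, the 21-patient row overstates the target-range percentage by about 9 to 11 points and understates stopping by about 9 to 12 points, and its mean of 12.2 patients should be about 10.0 to 10.6. The overdosing figure of 9.1% is not shown to be wrong (7.8 to 9.3% re-derived).

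This rests on the prior, overdose criterion, increment rule and cohort size as printed, and on a trial stopping when no dose meets the criterion.

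The documents do not show which input differed. As an assumption only, a rate of 0.05 in place of 0.10 at 0.3 mg gives 64.8 / 9.2 / 26.0% at cap 21 and 61.2 / 8.3 / 30.5% at cap 18, close to both published rows; 0.07 at 0.3 mg with 0.10 at 1 mg also comes near. A mistyped or changed input is therefore plausible but unconfirmed.

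The true design stops more often than stated, which is the conservative direction. It should be corrected as a misstated operating characteristic.

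**What to change.** Re-run Scenario 3 with the rates in Table 10.4: 2, or correct that table if other rates were simulated. Then update whatever the re-run changes: the Scenario 3 rows of Table 10.4: 3 at both caps, the 65.8% and 9.1% in the text, and the lower ends of the mean patient ranges (12.2 and 11.5). Add one sentence saying whether the MTD is declared only at the dose just given or at any recommended dose with 6 patients.

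The cost is one re-run and a few corrected figures. If the tabulated rates are kept, the stated Scenario 3 performance becomes less favourable on target percentage and shows more stopping. Nothing in the conduct of the trial changes.

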#### Maximum number of patients =18

If the maximum number of patients is chosen as 18, an early stopping of the trial would be more often required than above. In most cases, this would be due to reaching the maximum number of patients before an MTD could be determined. Still, the resulting operating characteristics are reasonable.

The mean patient numbers range from 11.5 patients (Scenario 3) to 17.6 patients (Scenario 4), and the maximum number of patients was 18. Again, the patient numbers are as expected and increase when moving away from the high-toxicity scenario.

Overall, by reviewing the metrics presented in [Table 10.4: 3](#), it can be seen that the model is generally conservative due to the overdose control criteria. In all scenarios, the probabilities of recommending a dose with true DLE rate being at least 25%,  $P(DLE \geq 25\%)$ , as MTD are much smaller than the probabilities of recommending a dose with true  $P(DLE) < 25\%$  as MTD.

R version 3.5.1 was used for data scenarios and simulations.

